 IQR: interquartile range. Body Mass Index (BMI): weight (kg) / [height (m)²].

Age is calculated as the number of full years between the date of birth and the date of signing the written patient authorization form.

Program code, date, time

Data extracted: DD.MM.YYYY

CONFIDENTIAL AND PROPRIETARY

Data MATRIX Ltd.

Page 25 of 79

P16-253 (CITRIN) _ STATISTICAL ANALYSIS PLAN _ FINAL 2.0 _ 16 Mar 2018

 AbbVie LLC
 P16-253 (CITRIN)

Table 1.4.2 Demographics and anthropometric characteristics (prior treatment groups)

 The core population
 Page X of X

| | Treatment-experienced (N=XX) | Naïve (N=XX) |
|--------------------------|---------------------------------|-----------------|
| Age (years) | ... | ... |
| Gender | ... | ... |
| Race | ... | ... |
| Weight (kg) | ... | ... |
| Height (cm) | ... | ... |
| BMI (kg/m ²) | ... | ... |

N: the number of subjects in the prior treatment groups of the core population. n: the number of valid measurements.

 IQR: interquartile range. Body Mass Index (BMI): weight (kg) / [height (m)²]. Percentages are calculated as (100 x n/N).

Age is calculated as the number of full years between the date of birth and the date of signing the written patient authorization form.

Program code, date, time

Data extracted: DD.MM.YYYY

P16-253 (CITRIN) _ STATISTICAL ANALYSIS PLAN _ FINAL 2.0 _ 16 Mar 2018

 AbbVie LLC
 P16-253 (CITRIN)

Table 1.4.3 Demographics and anthropometric characteristics (treatment-experienced groups)
 The core population
 Page X of X

| | PEG-INF alpha (N=XX) | non-PEG-INF alpha (N=XX) | INF all (N=XX) | Ribavirin (N=XX) |
|--------------------------|-------------------------|--------------------------------|-------------------|---------------------|
| Age (years) | ... | ... | ... | ... |
| Gender | ... | ... | ... | ... |
| Race | ... | ... | ... | ... |
| Weight (kg) | ... | ... | ... | ... |
| Height (cm) | ... | ... | ... | ... |
| BMI (kg/m ²) | ... | ... | ... | ... |

N: the number of subjects in the treatment-experienced groups of the core population. n: the number of valid measurements.

 IQR: interquartile range. Body Mass Index (BMI): weight (kg) / [height (m)²]. Percentages are calculated as (100 x n/N).

PEG-INF alpha: Pegylated Interferon alpha. non-PEG-INF alpha: Interferon alpha (non-pegylated).

Age is calculated as the number of full years between the date of birth and the date of signing the written patient authorization form.

Program code, date, time

Data extracted: DD.MM.YYYY

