P16-253 (CITRIN) _ STATISTICAL ANALYSIS PLAN _ FINAL 2.0 _ 16 Mar 2018

 AbbVie LLC
 P16-253 (CITRIN)

Table 1.4.4 Demographics and anthropometric characteristics (Child Pugh score groups)

 The core population
 Page X of X

| | Score 5 (N=XX) | Score 6 (N=XX) |
|--------------------------|-------------------|-------------------|
| Age (years) | ... | ... |
| Gender | ... | ... |
| Race | ... | ... |
| Weight (kg) | ... | ... |
| Height (cm) | ... | ... |
| BMI (kg/m ²) | ... | ... |

N: the number of subjects in the Child Pugh score groups of the core population. n: the number of valid measurements.

 IQR: interquartile range. Body Mass Index (BMI): weight (kg) / [height (m)²]. Percentages are calculated as (100 x n/N).

Age is calculated as the number of full years between the date of birth and the date of signing the written patient authorization form.

Program code, date, time

Data extracted: DD.MM.YYYY

Similar to table 1.4.1, tables for the target and the safety populations will be constructed:

Table 1.4.5 Demographics and anthropometric characteristics
Table 1.4.6 Demographics and anthropometric characteristics

P16-253 (CITRIN) _ STATISTICAL ANALYSIS PLAN _ FINAL 2.0 _ 16 Mar 2018
CHC disease characteristics

AbbVie LLC

P16-253 (CITRIN)

Table 1.5.1 CHC disease characteristics

The core population

Page X of X

| | | Total (N=XX) |
|--|-------|-----------------|
| Duration of HCV infection diagnosis (in years) | | |
| n | | XX |
| Mean | | XX.X |
| SD | | XX.XX |
| Median | | XX.X |
| IQR | | XX.X |
| Min | | XX |
| Max | | XX |
| Most likely mode of HCV infection | | |
| n | | XX |
| Blood transfusions | n (%) | XX (XX.X) |
| Dental procedures | n (%) | XX (XX.X) |
| ... | | ... |
| IL28B genotypes | | |
| rs12979860 | | |
| n | | XX |
| CC | n (%) | XX (XX.X) |
| CT | n (%) | XX (XX.X) |
| TT | n (%) | XX (XX.X) |
| Unknown | n (%) | XX (XX.X) |
| rs8099917 | | |
| n | | XX |
| GG | n (%) | XX (XX.X) |
| TG | n (%) | XX (XX.X) |
| TT | n (%) | XX (XX.X) |
| Unknown | n (%) | XX (XX.X) |

 N: the number of subjects in the core population. n: the number of valid measurements. Percentages are calculated as $(100 \times n/N)$.

Program code, date, time

Data extracted: DD.MM.YYYY

P16-253 (CITRIN) _ STATISTICAL ANALYSIS PLAN _ FINAL 2.0 _ 16 Mar 2018

 AbbVie LLC
 P16-253 (CITRIN)

Table 1.5.2 CHC disease characteristics (prior treatment groups)

 The core population
 Page X of X

| | Treatment-experienced (N=XX) | Naïve (N=XX) |

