| Ex-drinker | n (%) | XX (XX.X) | XX (XX.X) |
| None | n (%) | XX (XX.X) | XX (XX.X) |
| Yes, occasional | n (%) | XX (XX.X) | XX (XX.X) |
| Yes, regular | n (%) | XX (XX.X) | XX (XX.X) |
| Number of units/drinks per week | | | |
| n | | XX | XX |
| Mean | | XX.X | XX.X |
| SD | | XX.XX | XX.XX |
| Median | | XX.X | XX.X |
| IQR | | XX.X | XX.X |
| Min | | XX | XX |
| Max | | XX | XX |

N: the number of subjects in the core population. n: the number of valid measurements. Percentages are calculated as (100 x n/N).

Program code, date, time

Data extracted: DD.MM.YYYY

Similar to table 1.7.1, tables for the target and the safety populations will be constructed:

Table 1.7.5 Alcohol consumption
Table 1.7.6 Alcohol consumption

P16-253 (CITRIN) _ STATISTICAL ANALYSIS PLAN _ FINAL 2.0 _ 16 Mar 2018
Medical history

 AbbVie LLC
 P16-253 (CITRIN)

Table 1.8.1 Liver and/or CHC related co-morbidities

The core population

Page X of X

| System Organ Class Preferred Term [1] | Total (N=XX) |
|--|-----------------|
| | n (%) / E |
| Overall | XX (XX.X) / XX |
| System Organ Class 1 | XX (XX.X) / XX |
| Preferred Term A | XX (XX.X) / XX |
| Preferred Term A | XX (XX.X) / XX |
| ... | ... |
| System Organ Class 2 | XX (XX.X) / XX |
| Preferred Term C | XX (XX.X) / XX |
| Preferred Term D | XX (XX.X) / XX |
| ... | ... |
| ... | ... |

N: the number of subjects in the core population. n: the number of subjects within a specific category. E: number of medical history events reported. Liver and/or chc related co-morbidities were coded using MedDRA 20.1. Percentages are calculated from the number of subjects in the core population. System organ classes (SOC) and preferred terms (PT) within each SOC are sorted in descending order of Total frequency count.

[1] Within SOC patients may have reported more than one PT.

Program code, date, time

Data extracted: DD.MM.YYYY

P16-253 (CITRIN) _ STATISTICAL ANALYSIS PLAN _ FINAL 2.0 _ 16 Mar 2018

 AbbVie LLC
 P16-253 (CITRIN)

Table 1.8.2 Liver and/or CHC related co-morbidities (prior treatment groups)

The core population

Page X of X

| System Organ Class Preferred Term [1] | Treatment-experienced (N=XX) | | Naive (N=XX) | |
|--|---------------------------------|----------------|-----------------|----------------|
| | n (%) | / E | n (%) | / E |
| Overall | | XX (XX.X) / XX | | XX (XX.X) / XX |
| System Organ Class 1 | | XX (XX.X) / XX | | XX (XX.X) / XX |
| Preferred Term A | | XX (XX.X) / XX | | XX (XX.X) / XX |

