| Preferred Term A | | XX (XX.X) / XX | | XX (XX.X) / XX |
| ... | | ... | | ... |
| System Organ Class 2 | | XX (XX.X) / XX | | XX (XX.X) / XX |
| Preferred Term C | | XX (XX.X) / XX | | XX (XX.X) / XX |
| Preferred Term D | | XX (XX.X) / XX | | XX (XX.X) / XX |
| ... | | ... | | ... |
| ... | | ... | | ... |

N: the number of subjects in the core population. n: the number of subjects within a specific category. E: number of medical history events reported. Liver and/or chc related co-morbidities were coded using MedDRA 20.1. Percentages are calculated from the number of subjects in the core population. System organ classes (SOC) and preferred terms (PT) within each SOC are sorted in descending order of Treatment-experienced frequency count.

[1] Within SOC patients may have reported more than one PT.

Program code, date, time

Data extracted: DD.MM.YYYY

P16-253 (CITRIN) _ STATISTICAL ANALYSIS PLAN _ FINAL 2.0 _ 16 Mar 2018

 AbbVie LLC
 P16-253 (CITRIN)

Table 1.8.2 Liver and/or CHC related co-morbidities (treatment-experienced groups)

 The core population
 Page X of X

| System Organ Class Preferred Term [1] | PEG-INF alpha (N=XX) n (%) / E | non-PEG-INF alpha (N=XX) n (%) / E | INF all (N=XX) n (%) / E | Ribavirin (N=XX) n (%) / E |
|--|--------------------------------------|--|--------------------------------|----------------------------------|
| Overall | XX (XX.X) / XX | XX (XX.X) / XX | XX (XX.X) / XX | XX (XX.X) / XX |
| System Organ Class 1 | | | | |
| Preferred Term A | XX (XX.X) / XX | XX (XX.X) / XX | XX (XX.X) / XX | XX (XX.X) / XX |
| Preferred Term A | XX (XX.X) / XX | XX (XX.X) / XX | XX (XX.X) / XX | XX (XX.X) / XX |
| ... | ... | ... | ... | ... |
| System Organ Class 2 | | | | |
| Preferred Term C | XX (XX.X) / XX | XX (XX.X) / XX | XX (XX.X) / XX | XX (XX.X) / XX |
| Preferred Term D | XX (XX.X) / XX | XX (XX.X) / XX | XX (XX.X) / XX | XX (XX.X) / XX |
| ... | ... | ... | ... | ... |
| ... | ... | ... | ... | ... |

N: the number of subjects in the core population. n: the number of subjects within a specific category. E: number of medical history events reported.
 PEG-INF alpha: Pegylated Interferon alpha. non-PEG-INF alpha: Interferon alpha (non-pegylated).

Liver and/or chc related co-morbidities were coded using MedDRA 20.1. Percentages are calculated from the number of subjects in the core population.

System organ classes (SOC) and preferred terms (PT) within each SOC are sorted in descending order of INF all frequency count.

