[1] Within SOC patients may have reported more than one PT.

Program code, date, time

Data extracted: DD.MM.YYYY

P16-253 (CITRIN) _ STATISTICAL ANALYSIS PLAN _ FINAL 2.0 _ 16 Mar 2018

 AbbVie LLC
 P16-253 (CITRIN)

Table 1.8.2 Liver and/or CHC related co-morbidities (Child Pugh score groups)

 The core population
 Page X of X

| System Organ Class Preferred Term [1] | Score 5 (N=XX) | Score 6 (N=XX) |
|--|-------------------|-------------------|
| | n (%) / E | n (%) / E |
| Overall | XX (XX.X) / XX | XX (XX.X) / XX |
| System Organ Class 1 | XX (XX.X) / XX | XX (XX.X) / XX |
| Preferred Term A | XX (XX.X) / XX | XX (XX.X) / XX |
| Preferred Term A | XX (XX.X) / XX | XX (XX.X) / XX |
| ... | ... | ... |
| System Organ Class 2 | XX (XX.X) / XX | XX (XX.X) / XX |
| Preferred Term C | XX (XX.X) / XX | XX (XX.X) / XX |
| Preferred Term D | XX (XX.X) / XX | XX (XX.X) / XX |
| ... | ... | ... |
| ... | ... | ... |

N: the number of subjects in the core population. n: the number of subjects within a specific category. E: number of medical history events reported. Liver and/or chc related co-morbidities were coded using MedDRA 20.1. Percentages are calculated from the number of subjects in the core population. System organ classes (SOC) and preferred terms (PT) within each SOC are sorted in descending order of score 5 frequency count.

[1] Within SOC patients may have reported more than one PT.

Program code, date, time

Data extracted: DD.MM.YYYY

Similar to table 1.8.1, tables for the target and the safety populations will be constructed:

Table 1.8.5 Liver and/or CHC related co-morbidities
Table 1.8.6 Liver and/or CHC related co-morbidities

P16-253 (CITRIN) _ STATISTICAL ANALYSIS PLAN _ FINAL 2.0 _ 16 Mar 2018

Similar to tables 1.8.X, tables for the other co-morbidities will be constructed:

for the core population

Table 1.9.1 Other co-morbidities

Table 1.9.2 Other co-morbidities (prior treatment groups)

Table 1.9.3 Other co-morbidities (treatment-experienced groups)

Table 1.9.4 Other co-morbidities (Child Pugh score groups)

for the target and safety populations

Table 1.9.5 Other co-morbidities

Table 1.9.6 Other co-morbidities

P16-253 (CITRIN) _ STATISTICAL ANALYSIS PLAN _ FINAL 2.0 _ 16 Mar 2018
Co-infections

AbbVie LLC

P16-253 (CITRIN)

Table 1.10.1 Co-infections

The core population

Page 1 of 1

| Diagnosis | Total (N=XX) |
|------------------------------------|-----------------|
| | n (%) |
| Hepatitis B | XX (XX.X) |

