P16-253 (CITRIN)

Table 1.12.2 Prior Medications for CHC (prior treatment groups)

The core population

Page X of X

| Pharmacological subgroup WHODD chemical substance | Treatment-experienced (N=XX) n (%) / E | Naïve (N=XX) n (%) / E |
|--|--|------------------------------|
| Total [1] | XX (XX.X) /XX | |
| XXXXXXXXXXXXXXXXXXXXXXXXXXXX | XX (XX.X) /XX | |
| XXXXXXXXXXXXXXXXXXXXXXXXXXXX | XX (XX.X) /XX | |
| XXXXXXXXXXXXXXXXXXXXXXXXXXXX | XX (XX.X) /XX | |
| ... | ... | |
| XXXXXXXXXXXXXXXXXXXXXXXXXXXX | XX (XX.X) /XX | |
| XXXXXXXXXXXXXXXXXXXXXXXXXXXX | XX (XX.X) /XX | |
| ... | ... | |
| ... | ... | |

N: the number of subjects in the core population. n: the number of subjects within a specific category. Percentages are calculated as $(100 \times n/N)$.
 E: number of medical history events reported. Prior medications were coded using WHODD version Jun 2015. Each subject is only counted once per preferred name and once per ATC group. ATC group and preferred names within each ATC group are sorted in descending order of Treatment-experienced frequency count.
 [1] The Total line displays the number (n) and the proportion (%) of patients, who have at least one prior medication prescription, and the total number of prior medication prescriptions.

Program code, date, time

Data extracted: DD.MM.YYYY

P16-253 (CITRIN) _ STATISTICAL ANALYSIS PLAN _ FINAL 2.0 _ 16 Mar 2018

AbbVie LLC

P16-253 (CITRIN)

Table 1.12.3 Prior Medications for CHC (treatment-experienced groups)

The core population

Page X of X

| Pharmacological subgroup WHODD chemical substance | PEG-INF alpha (N=XX) n (%) / E | non-PEG-INF alpha (N=XX) n (%) / E | INF all (N=XX) n (%) / E | Ribavirin (N=XX) n (%) / E |
|--|--------------------------------------|--|--------------------------------|----------------------------------|
| Total [1] | XX (XX.X) /XX | | | |
| XXXXXXXXXXXXXXXXXXXXXXXXXXXX | XX (XX.X) /XX | | | |
| XXXXXXXXXXXXXXXXXXXXXXXXXXXX | XX (XX.X) /XX | | | |
| XXXXXXXXXXXXXXXXXXXXXXXXXXXX | XX (XX.X) /XX | | | |
| ... | ... | | | |
| XXXXXXXXXXXXXXXXXXXXXXXXXXXX | XX (XX.X) /XX | | | |
| XXXXXXXXXXXXXXXXXXXXXXXXXXXX | XX (XX.X) /XX | | | |
| ... | ... | | | |
| ... | ... | | | |

N: the number of subjects in the core population. n: the number of subjects within a specific category. Percentages are calculated as $(100 \times n/N)$.
 PEG-INF alpha: Pegylated Interferon alpha. non-PEG-INF alpha: Interferon alpha (non-pegylated).

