E: number of medical history events reported. Prior medications were coded using WHODD version Jun 2015. Each subject is only counted once per preferred name and once per ATC group. ATC group and preferred names within each ATC group are sorted in descending order of INF all frequency count.

[1] The Total line displays the number (n) and the proportion (%) of patients, who have at least one prior medication prescription, and the total number of prior medication prescriptions.

Program code, date, time

Data extracted: DD.MM.YYYY

P16-253 (CITRIN) _ STATISTICAL ANALYSIS PLAN _ FINAL 2.0 _ 16 Mar 2018

 AbbVie LLC
 P16-253 (CITRIN)

Table 1.12.4 Prior Medications for CHC (Child Pugh score groups)

 The core population
 Page X of X

| Pharmacological subgroup WHODD chemical substance | Score 5 (N=XX) n (%) / E | Score 6 (N=XX) n (%) / E |
|--|--------------------------------|--------------------------------|
| Total [1] | XX (XX.X) /XX | |
| XXXXXXXXXXXXXXXXXXXXXXXXXXXXXX | XX (XX.X) /XX | |
| XXXXXXXXXXXXXXXXXXXXXXXXXXXXXX | XX (XX.X) /XX | |
| XXXXXXXXXXXXXXXXXXXXXXXXXXXXXX | XX (XX.X) /XX | |
| ... | ... | |
| XXXXXXXXXXXXXXXXXXXXXXXXXXXXXX | XX (XX.X) /XX | |
| XXXXXXXXXXXXXXXXXXXXXXXXXXXXXX | XX (XX.X) /XX | |
| ... | ... | |
| ... | ... | |

N: the number of subjects in the core population. n: the number of subjects within a specific category. Percentages are calculated as $(100 \times n/N)$.
 E: number of medical history events reported. Prior medications were coded using WHODD version Jun 2015. Each subject is only counted once per preferred name and once per ATC group. ATC group and preferred names within each ATC group are sorted in descending order of score 5 frequency count.

[1] The Total line displays the number (n) and the proportion (%) of patients, who have at least one prior medication prescription, and the total number of prior medication prescriptions.

Program code, date, time

Data extracted: DD.MM.YYYY

Similar to table 1.12.1, tables for the target and the safety populations will be constructed:

Table 1.12.5 Prior Medications for CHC
Table 1.12.6 Prior Medications for CHC

P16-253 (CITRIN) _ STATISTICAL ANALYSIS PLAN _ FINAL 2.0 _ 16 Mar 2018

Similar to tables 1.12.X, tables for the concurrent medications for CHC will be constructed:

for the core population

Table 1.13.1 Concurrent Medications for CHC
Table 1.13.2 Concurrent Medications for CHC (prior treatment groups)

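### Subgroup shells for co-morbidities, medication and other baseline data name the whole core population as percentage denominator, in conflict with the subgroup N in their own column headers

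*SAP*

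**What the plan says.** SAP section 8 asks for baseline characteristics, concurrent illnesses and medications in the CP, both overall and by CP analysis group (Child Pugh score 5 or 6; treatment-experienced or naïve). The shells in SAP section 18 carry this out with three kinds of subgroup table: prior treatment groups, prior-drug groups among the experienced, and Child Pugh groups.

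- **Co-morbidities.** Three subgroup shells are all headed Table 1.8.2 (the table list in section 16.1 numbers them 1.8.2 to 1.8.4). Each defines N as the core population and adds a separate sentence: "Percentages are calculated from the number of subjects in the core population". Tables 1.9.x inherit this: "Similar to tables 1.8.X, tables for the other co-morbidities will be constructed".
- **Prior medication, 1.12.2 to 1.12.4.** The footnote reads "N: the number of subjects in the core population. n: the number of subjects within a specific category", with the percentage as 100 x n/N. Tables 1.13.x inherit it: "Similar to tables 1.12.X, tables for the concurrent medications for CHC will be constructed".
- **Tables 1.6, 1.7, 1.10 and 1.11.** The subgroup shells also define N as the core population and use 100 x n/N.
- **Column headers.** All of these shells print a separate N over each subgroup column, for example "Treatment-experienced (N=XX) n (%) / E" in Table 1.12.2.
- **Demographics.** For the same kinds of column, Table 1.4.2 says "N: the number of subjects in the prior treatment groups of the core population" and Table 1.4.4 says "N: the number of subjects in the Child Pugh score groups of the core population".

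SAP section 7.1 bases percentages on subjects with non-missing data, but only where nothing else is specified.

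**The concern.** A percentage in a subgroup column should give the share of that subgroup with the condition or drug. Dividing by the whole CP gives the share of the CP that is both in the subgroup and affected, which depends on how large the subgroup is. Two groups with the same prevalence then look different, and the smaller group looks healthier or less medicated than it is.

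Co-morbidities and concomitant medications are a stated secondary objective (protocol section 8.2.2, SAP section 3.1), and the breakdown by analysis group is what SAP section 8 requires. A programmer working from the shells has two rules for identical columns, and in the 1.8.x shells the explicit sentence points to the wrong one.

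**Working it through.** The plan has no figure to reproduce: the shells hold only placeholders, and the 60 patients are not a calculated sample size. The check therefore compares the wording and then works out what the literal rule does.

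**Wording**

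| Shells | N in column header | N in footnote | Percentage rule |
|---|---|---|---|
| 1.4.2 to 1.4.4 | per column | subgroup of the CP | 100 x n/N |
| 1.8.x subgroup, inherited by 1.9.x | per column | CP | from the CP, stated outright |
| 1.12.2 to 1.12.4, inherited by 1.13.x | per column | CP | 100 x n/N |
| Subgroup shells of 1.6, 1.7, 1.10, 1.11 | per column | CP | 100 x n/N |

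In the 1.8.x shells the denominator sentence does not use the symbol N, so reading N as the column size does not remove the conflict. In the other conflicting shells N has two meanings. The section 7.1 default does not settle it, because these footnotes do specify something else. The 1.8.x sentence matches the one under the overall Table 1.8.1, where the CP is correct. In the subgroup copies the sort-order sentence was adapted to the new columns and the denominator sentence was not.

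**Effect if the footnotes are followed**

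Let n_g be the count in subgroup g, N_g the subgroup size and N_CP the size of the CP.

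- Subgroup percentage: 100 x n_g / N_g
- Footnote percentage: 100 x n_g / N_CP
- Ratio of footnote to subgroup percentage: N_g / N_CP

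Inputs:

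- N_CP = 60 is an assumption, taken from the planned number of patients (SAP, Sample size).
- The 33/27 split is an assumption, using the 55% treatment-experienced share that protocol section 7.0 reports for the earlier 60-patient trial: 0.55 x 60 = 33.
- The 48/12 split is an assumption, to show a less balanced case such as Child Pugh 5 against 6.

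The documents give no subgroup sizes for this study.

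One third affected in each group:

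| Split | Counts | Subgroup denominators | Footnote denominator |
|---|---|---|---|
| 33 / 27 | 11 / 9 | 33.3% / 33.3% | 11/60 = 18.3% / 9/60 = 15.0% |
| 48 / 12 | 16 / 4 | 33.3% / 33.3% | 16/60 = 26.7% / 4/60 = 6.7% |

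The scaling factors are 12/60 = 0.20, 27/60 = 0.45, 33/60 = 0.55 and 48/60 = 0.80. A true 50% in a subgroup of 12 (6 patients) prints as 6/60 = 10.0%; in a subgroup of 48 (24 patients) it prints as 24/60 = 40.0%.

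**The case against.** The best defence is that nothing here shows the tables will be divided wrongly. Every subgroup column has its own N, and in the medication shells the formula is 100 x n/N beneath that N, so a sensible programmer may well use it. The footnotes look like text carried over from the overall tables, not a chosen denominator. The secondary objective concerns cirrhotic patients in general and is met by the overall tables, whose denominator is correct. The subgroup tables are untested description, and since n and the column N are both printed, a reader can recompute any percentage.

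Much of this stands. A reader might infer that the SAP settles on dividing by the whole CP; it does not, because header and footnote contradict each other. A reader might also infer that every subgroup percentage would be too low. Zero counts do not change (prior CHC medication in naïve patients is the obvious case), nor would a subgroup that made up the whole CP. And it is tempting to treat all of Tables 1.5.2 to 1.5.4 as sound models, but 1.5.3 (prior-drug columns) and 1.5.4 (Child Pugh columns) both define N by the prior treatment groups, so their footnotes need correcting too.

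What does not stand is the inference that no change is needed. The 1.8.x sentence is an explicit instruction, and a likely innocent origin does not stop it from being followed.

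**Conclusion.** The footnotes are wrong as written, and the point is minor. They name a denominator that contradicts the column headers and the demographics shells. If followed, they scale each non-zero subgroup percentage by N_g/N_CP, a factor of 0.20 to 0.80 for subgroups of 12 to 48 in an assumed CP of 60. The direction of the error follows from the rule alone; its size depends on subgroup sizes that the documents do not give.

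The effect is confined to descriptive baseline subgroup tables. The overall tables use the CP correctly. A reader might worry that the response rates are touched, but the SVR12 percentage shells have a single Total column and are unaffected.

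**What to change.** - In the subgroup shells of Tables 1.6 to 1.10, 1.12 and 1.13, define N as the number of subjects in the column's subgroup of the core population and base percentages on that column N. Where section 7.1 is meant to apply, use subjects with non-missing data in that column and say so. Tables 1.6 and 1.7 need this choice most, because there n is defined as valid measurements.
- Delete the core-population denominator sentence from the 1.8.x subgroup shells.
- In the subgroup shells of Table 1.11, base percentages on subjects in the column with a valid result. SAP section 8.4 limits the CD4 and HIV-RNA results to HIV co-infected patients, so dividing by the full subgroup would still mislead.
- In Tables 1.5.3 and 1.5.4, correct the N footnote to name the prior-drug groups and the Child Pugh groups respectively.

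The cost is editing the footnotes and checking the denominator in the table programs. No new data are needed and no effectiveness analysis changes.
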